10. DISPOSITION AND WITHDRAWALS

All patients who signed ICF will be involved in the analysis of disposition and withdrawals being described in this section for this study.

The number of patients who signed ICF for the study, screen failed patients along with the reason for screen failure, patients who passed screening but withdraw before the first dose of study treatment will also be summarized.

The number of patients included/excluded from each analysis set as well as the reason(s) for exclusion (as described in Section 6) will also be summarized by dose level in escalation phase and by disease cohort in dose expansion phase. A corresponding by-patient listing will also be provided.

The number and percentage of patients who completed, discontinued from study medication and reasons for study medication discontinuation will be presented for each dose level, by disease cohort, and overall for the SAS.

Reasons for discontinuation of study medication will be presented as recorded on the CRF page "End of Treatment".

The number and percentage of patients who completed, discontinued from study and reasons for study discontinuation will be presented for each dose level, disease cohort, and overall for the SAS. Reasons for study discontinuation will be presented as recorded on the CRF page "End of Study".

A patient listing will be generated to include site, patient number, informed consent information (date), screening date, first and last study medication dosing date, duration of study medication, study medication discontinuation information (date and reason), and end of study information (date, status, and reason for discontinuation if applicable) will be provided. Besides, the violation of inclusion/exclusion criteria will also be listed for ENR analysis set.

Major protocol deviations related to study inclusion or exclusion criteria, conduct of the trial, patient management, or patient assessment will be listed.

[figure not shown]
11. DEMOGRAPHIC AND OTHER BASELINE CHARACTERISTICS

Demographic data and other baseline characteristics will be summarized by dose cohort in dose escalation phase and by disease cohort in dose expansion phase for the SAS. Data listing will also be provided.

The following demographic and other baseline characteristics will be reported and listed for this study:

- Age (years) - Calculated relative to date of ICF
- Age group
 - <65 years
 - ≥65 years
- Gender

CCI

- Male
 - Female
 - With Child Bearing Potential
 - Without Child Bearing Potential
 - Undifferentiated
 - Unknown
- Race
 - American Indian or Alaska Native
 - Asian
 - Black or African American
 - Native Hawaiian or Other Pacific Islanders
 - White
 - Other
 - Ethnicity
 - Hispanic or Latino
 - Not Hispanic or Latino
 - Not Reported
 - Unknown
 - Baseline Weight (kg)
 - Baseline Height (m)
 - Baseline BMI (kg/m²)
 - Baseline ECOG performance status (refer Section 17.6.1)
 - 0
 - 1
 - >1
 - Baseline Sum of Diameters of Target Lesions (mm)

Other baseline characteristics related to the oncology history will be described in Section 12.

11.1. DERIVATIONS

- $BMI \text{ (kg/m}^2\text{)} = \text{weight (kg)} / \text{height (m)}^2$
- Age (Years) = (Date of Informed Consent Signed – Date of Birth + 1)/365.25

12. MEDICAL HISTORY AND ONCOLOGY HISTORY

Pre-existing medical conditions are recorded on the “Medical History” CRF page.

[figure not shown]
Medical history (excluding oncology history) will be summarized by system organ class (SOC) and preferred term (PT) for the SAS set. Medical Dictionary for Regulatory Activities (MedDRA) central coding dictionary, Version 23.0 (MedDRA 23.0) or higher will be used for coding. Number and percentage will be presented in frequency tables by dose cohort in dose escalation phase and disease cohort in dose expansion phase, and ordered by primary SOC and PT in descending order of the frequency in total within each category. For SOCs or PTs with the same frequency in total, categories will be sorted alphabetically.

Oncology history information will be captured on CRF page “Oncology History” and the following oncology history information will be summarized:

- Type of malignancy
- Duration of malignancy (years) – Calculated relative to date of ICF
- Time since the initial diagnosis to first administration of study medication (years) – Calculated relative to date of first administration of study medication
- Stage of the disease at the time of initial diagnosis
 - Stage I
 - Stage II
 - Stage III
 - Stage IV
- Metastasis Status (Yes, No)
- Duration of Metastasis (Years) – Calculated relative to date of ICF
- Prior oncology treatments
 - Oncology Chemotherapy and Medication
 - Oncology Radiation Therapy
 - Oncology Surgery and Procedures

Medical history and oncology history will be listed for the SAS.

CCI

12.1. DERIVATIONS

- Duration of malignancy (years) = (Date of Informed Consent Signed – Date of first confirmed malignancy + 1)/365.25.
- Time since the initial diagnosis to first administration of study medication (years) = (Date of first administration of study medication – Initial primary diagnosis date for solid tumor + 1)/365.25.
- Duration of metastasis (years) = (Date of Informed Consent Signed – Date of metastasis observed + 1)/365.25.

13. MEDICATIONS AND PROCEDURES

Prior medications are medications which ended prior to the first dosing date of study medication. Concomitant medications/procedures are medications/procedures which started no later than 30+7 days following the last dose administration, and ended on or after the date of first dose of medication or were ongoing at the end of the study. Relevant information is collected on CRF page “Prior and Concomitant Medications”, “Concomitant Procedures”. Prior and concomitant medications will be coded using World Health Organization Drug Dictionary Enhanced (WHO-DDE), version Mar2020 or latest version. Anatomical Therapeutic Chemical (ATC) level 2 classification and Preferred term (PT) will be used for coding.

Concomitant medications will be summarized by ATC level 2 and PT for each dose cohort in dose escalation phase and each disease cohort in dose expansion phase for the SAS. PT will be sorted in descending frequency of the total number of patients with at least one medication in the corresponding category, PTs will be presented alphabetically for PTs of the same total frequency.

Concomitant procedures will be coded by MedDRA 23.0 or higher and will be presented by PT by dose cohort in dose escalation phase and by disease cohort in dose expansion phase. PT will be sorted in descending frequency of the total number of patients with at least one procedure in the corresponding category, PTs will be presented alphabetically for PTs of the same total frequency.

Prior and concomitant medications will be presented in listings with flag to differentiate whether the medication was prior medication or concomitant medication. Similar for prior and concomitant procedures information.

14. ONCOLOGY THERAPIES

Prior oncology therapies include oncology chemotherapy and medication, oncology radiotherapy, and oncology surgery and procedures. Oncology chemo therapy and medication will be captured on “Oncology Chemotherapy and

CCI

Oncology Medication" CRF page, oncology radiotherapy will be captured on "Oncology Radiotherapy" CRF page, and oncology surgery and procedures will be captured on "Oncology Surgery and Procedure" CRF page. Prior oncology chemotherapies and medications will be coded using WHO-DDE, version Mar2020 or latest version, and will be presented by ATC level 2 classification and PTs for each dose cohort in dose escalation phase and each disease cohort in dose expansion phase for the SAS. PT will be sorted in descending frequency of the total number of patients with at least one condition in the corresponding category, PTs will be presented alphabetically for PTs of the same total frequency. In addition, number and percentage of patients who received prior oncology chemotherapies and medications, number of regimens, best response, treatment failure information and appearance of adverse reaction with severity above grade 3 will be summarized for prior oncology chemotherapies and medications.

The number and percentage of patients who received prior oncology radiotherapy, purpose, best response, and appearance of adverse reaction with severity above grade 3 will be summarized for prior oncology radiotherapy. Prior oncology surgery and procedure will be coded using MedDRA 23.0 or higher, and will be summarized by SOC and PT for each disease cohort in dose expansion phase and dose escalation phase for the SAS. SOC and PT will be sorted in descending frequency of the total number of patients with at least one condition in the corresponding category, SOCs/PTs will be presented alphabetically for SOCs/PTs of the same total frequency. Since on-study oncology therapies are not allowed, oncology therapies will be classified and reported as prior. Any concurrent oncology therapy will be considered and reported as protocol deviation.

All the oncology therapies as well as general therapies will be listed by disease cohort in dose expansion phase and dose escalation phase.

Oncology chemotherapy and oncology medication, oncology radiotherapy, and oncology surgery and procedure will be listed for SAS. Oncology surgery and procedure will be listed for SAS and will be presented separately from concomitant procedures.

[figure not shown]
New anti-tumor therapy is defined as any anti-tumor therapy started after first dose of study medication. New anti-tumor therapy will be flagged in the listing of oncology medication/radiotherapy/surgery.

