7.3.2 Excluded Therapies

Any therapy intended for the treatment of cancer (with the exceptions as noted above), whether currently marketed or experimental, is prohibited. This includes, but is not limited to, the following: chemotherapy, hormonal therapy, biologic therapy, radiotherapy, or herbal therapy.

Prophylactic antiemetic, granulocyte colony stimulating factors, granulocyte macrophage colony-stimulating factors, platelet simulating factors or erythropoietin are not allowed during DLT observation period in the dose escalation phase.

Concomitant use with acid-reducing agents (eg, proton pump inhibitors, histamine receptor antagonists, antacids) in Cycle 1 of the dose escalation phase should be avoided as those agents may interfere with reliable identification of the MTD and/or RP2D. However, use of gastroduodenal mucosal protective agents, such as sucralfate, is allowed.

Concomitant use of SSAs by patients with non-functioning pNETs or NETs is not permitted, and must have been discontinued at least 4 weeks before administration of the first dose of study drug.

Concomitant use of medications that are known to cause QTcF prolongation, and/ or Torsades des Pointes. See [Appendix 6](#) for a table of current medications in this category, and also consult the current list at <http://www.qtdrugs.org/>, which is updated continuously, for the most complete information.

Palliative radiation for symptom control is allowed provided it does not compromise tumor assessments of target lesions. However, surufatinib treatment should be suspended during the radiation period and resumed at least 7 days after radiation only after meeting the following criteria:

- Radiation related toxicities resolve to \leq Grade 2;
- No disease progression observed.

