16.1. EFFICACY VARIABLE(S) & DERIVATION(S)

16.1.1. Progression-Free Survival

Progression-free survival (PFS) is defined as the time (in months) from the start date of study medication (Day 1) until the date of objective disease progression as defined by RECIST Version 1.1 or death (by any cause in the absence of progression), whichever occurred earlier.

The PFS time will always be derived based on scan/assessment dates and not based on visit dates. RECIST

CCI

assessments/scans contributing towards a particular visit, which consists of assessment for “Non-Target lesions”, “Target lesions”, and “New lesions”, may be performed on different dates. The following rules will be applied:

- Date of progression will be determined based on the earliest of the dates of the radiological component that triggered the progression.
- When censoring a patient for PFS the patient will be censored at the latest of the dates contributing to a particular overall visit assessment.

If a patient has not experienced progressive disease (PD) or died before the end of study for any reason, progression-free survival will be censored at the date of the last evaluable tumor assessment on or prior to the PD, which is not necessarily confirmed.

Three additional rules apply to PFS only:

[figure not shown]
- If a patient misses two or more consecutive tumor assessment visits, and showed PD or death afterwards, PFS will be censored at the date of last tumor assessment prior to the consecutive missed visits. Two consecutive missed/non-evaluable tumor assessment visit window is calculated as $2*(8 \text{ weeks}+1\text{week window time})$, which is 126 days.
- If a patient reports no baseline tumor assessments or has no evaluable tumor assessment visits after the first dose of study medication, PFS will be censored at the start date of study medication unless they die within two consecutive tumor assessments since the first dose of study medication, i.e., PFS=1 day.
- Of note that tumor assessments after the first new anti-cancer treatment (same day inclusive) will be considered inadequate. If a patient starts new anti-tumor therapy initiated prior to documented disease progression or death on study, PFS will be censored at the date of the last tumor assessment prior to or on the date of new anti-tumor therapy.

See Table 1 for the detailed information of event/censoring rules for PFS:

Table 1: PFS Events/censoring rules

Description	Event/Censor	Date of Event/Censor

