17.1. ADVERSE EVENTS

An adverse event (AE) is any unfavorable and unintended sign, symptom, or disease temporally associated with the use of the investigational medicinal product or other protocol-imposed intervention, regardless of attribution. Relevant information is recorded on CRF page “Adverse Event/Serious Adverse Event”.

If a persistent AE becomes more severe, it should be recorded again with the updated severity. All recurrent AEs (AEs that occurs and resolves between patient evaluation time points and subsequently recurs) should be recorded on “Adverse Event/Serious Adverse Event” CRF.

[figure not shown]
A pre-existing medical condition should be recorded as an AE or SAE only if the frequency, severity, or character of the condition worsens during the study.

After informed consent, but prior to initiation of study medications, only SAEs caused by a protocol-mandated intervention will be collected.

After initiation of study medications, all AEs and SAEs regardless of attribution will be collected until 37 days (30 days + 7 days window) following the last administration of study medication or study discontinuation/termination, whichever is later. After this period, investigators should report only SAEs that are felt to be related to prior study treatment.

Treatment-emergent AEs (TEAEs) are defined as AEs that started or worsened in severity on or after the first administration date of study medication and no later than 30 (+7) days after the last administration date of study

CCI

medication or initiation of new anti-tumor therapy (whichever occurs first).

An exception is that study medication related SAEs collected later than 37 days after the last dosing date will be treated as TEAEs.

If the start date coincides with the reference start date, a query “Prior/ post 1st dose” will be used to identify TEAEs (only when ‘Post 1st dose’ will be considered as TEAE, if ‘Prior’ then not TEAE). When there is no definite answer to the query, the AE will be considered as a TEAE. See section 8.2 for handling of partial dates for AEs. In the case where it is not possible to classify an AE as treatment-emergent or not, the AE will be classified by the worst case; i.e. treatment-emergent.

If a subject reports a TEAE more than once in the SOC/PT, the TEAE with highest severity will be used in the corresponding summaries.

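### SAP 14 makes no exception for the palliative radiation that Protocol 7.3.2 permits, so read literally it triggers PFS censoring, loss of later scans and closure of the TEAE window

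*SAP*

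**What the plan says.** **Protocol 7.3.2** bars treatment directed at the cancer, listing "chemotherapy, hormonal therapy, biologic therapy, radiotherapy, or herbal therapy", and then makes an allowance: "Palliative radiation for symptom control is allowed provided it does not compromise tumor assessments of target lesions". The patient is expected to stay in the treatment phase, since "surufatinib treatment should be suspended during the radiation period and resumed at least 7 days after radiation", subject to recovery from radiation toxicity and no progression having been seen.

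**SAP 14** starts from a different premise: "Since on-study oncology therapies are not allowed, oncology therapies will be classified and reported as prior". It adds that any concurrent oncology therapy is to be reported as a deviation. It then gives the definition at issue, "New anti-tumor therapy is defined as any anti-tumor therapy started after first dose of study medication", and says that "New anti-tumor therapy will be flagged in the listing of oncology medication/radiotherapy/surgery". The allowance in Protocol 7.3.2 is not mentioned. SAP 4.4, which lists changes from the protocol, names only additional ECG analyses.

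**The term is then used in four places:**
- SAP 16.1.1 and Table 1 (PFS): censoring at the last scan before the new therapy, because "tumor assessments after the first new anti-cancer treatment (same day inclusive) will be considered inadequate".
- SAP 16.1.2 (best overall response): the same exclusion of later scans, which carries into ORR and DCR.
- SAP 16.1.6 (duration of response): a responder with no progression before new treatment takes the PFS censoring time.
- SAP 17.1 (TEAEs): the window runs to 30 (+7) days after the last administration of study "medication or initiation of new anti-tumor therapy (whichever occurs first".

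**The concern.** The two documents disagree on whether any on-study radiotherapy is allowed, and the disagreement feeds derivations rather than only a listing. The SAP definition is anchored to first dose, not to the end of treatment, so a programmer working from SAP 14 would flag a palliative radiation record dated in the middle of treatment.

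The primary endpoint in every expansion arm is a PFS rate at a landmark, and the arms are small: 30, 15 and 15 patients, and sarcoma subtypes of 10 or 5. A few patients handled the wrong way can move an estimate visibly. SAP 16 keeps scans on schedule during interruptions, so the data would be collected and then not used. SAP 16.4 plans no sensitivity analysis that would show the effect. On safety, events arising after surufatinib is resumed could be missing from the TEAE tables although the patient is on drug.

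**Working it through.** **1. Trace of the rule.** Take a patient irradiated at week 6 under Protocol 7.3.2 who resumes surufatinib. Scans fall at Cycle 2 Day 1 (week 4) and every 8 weeks after that (Protocol 5.1.2): weeks 4, 12, 20.
- SAP 14: therapy after first dose, in the radiotherapy listing, no exception. Flagged as new, and a deviation.
- SAP 16.1.1: PFS censored at the week-4 scan. Scans at weeks 12 and 20 do not count.
- SAP 17.1: the sentence has two readings. The window closes at the start of radiation (week 6), or 30 (+7) days after it: day 42 + 37 = day 79, about week 11. On both, events during resumed dosing can fall outside. The exception for drug-related SAEs covers only those collected more than 37 days after the last dose, so it does not bring these back.

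**2. The plan's own figures.** Protocol 10.1 sets, for Arms B and C, at least 6 event-free patients of 15. Exact binomial:
- P(X ≥ 6 | n = 15, p = 0.50) = 1 − 4944/32768 = 84.9% (stated 84.9%).
- P(X ≥ 6 | n = 15, p = 0.19) = 4.9% (stated 4.9%).

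The Arm A figures (90.6%, 2.8%) and the sarcoma subtype figures (83.3%, 7%) also reproduce. None of them allows for patients made uncountable by this rule.

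**3. Upward case.** Assumptions: 15 patients, 5 event-free at 11 months, all other events after week 4, and m of the later progressors irradiated early and censored at week 4. The Kaplan-Meier estimate at 11 months is 5/(15 − m).

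| m | Estimate | Patients event-free |
|---|---|---|
| 0 | 5/15 = 33.3% | 5 |
| 2 | 5/13 = 38.5% | 5 |
| 3 | 5/12 = 41.7% | 5 |

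The count stays at 5, below 6, in every row.

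**4. Downward case.** Arm A, landmark 16 weeks, 12 of 30 event-free, no events before week 4. One of the 12 is irradiated at week 6 and progresses at week 20. True estimate: 12/30 = 40.0%. With censoring at week 4: 11/29 = 37.9%. The same holds in Arm D, where 4 months is 4 × 30.4375/7 = 17.4 weeks, also before week 20.

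**5. Count rule.** If k patients in Arm B or C become uncountable independently of outcome and the threshold stays at 6, the chance of meeting it at a true rate of 50% falls from 84.9% to:
- k = 1: 1 − 3473/16384 = 78.8%
- k = 2: 1 − 2380/8192 = 70.9%
- k = 3: 1 − 1586/4096 = 61.3%

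**6. Range for the upward case.** A simulation used exponential PFS, with a share q of patients who would progress before the landmark irradiated at a random earlier time and censored at the last scan. For q = 5, 10 and 20% it moves the mean estimate in Arms B and C from 50% to about 52, 53 and 56%, and in Arm A from 40% to about 41, 43 and 46%. Only progressors are irradiated in this set-up, so the direction is built in. The documents give no value for m, k or q.

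**The case against.** The strongest reply is that no sentence calls palliative radiation anti-tumor therapy. Protocol 7.3.2 sets symptom control apart from treatment of the cancer. Protocol 5.6 makes other antitumor treatment a reason to stop study drug, so radiation followed by resumption cannot be what the protocol means by that term. SAP 8.2 says that subsequent therapy records should generally start after end of treatment or progression. SAP 13 has a separate page for concomitant procedures, and if palliative radiation is entered there it may escape the flag. SAP 6.5 has the study team classify important deviations before lock.

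Most of this stands as evidence that the overlap is unintended, and the CRF page used is unknown. It does not limit the definition. SAP 8.2 is guidance for imputing dates, and its own table handles therapy that starts before both reference dates. If the form used decides the outcome, that too needs a rule.

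It is also fair to say that carrying PFS and response through radiation is an analysis choice which the documents do not dictate. The SAP still has to make it openly.

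Three stronger readings are tempting and not supported:
- *The rule inflates the primary PFS rate.* Only for patients who would have progressed before the landmark; step 4 shows the reverse. No passage says that irradiated patients have a worse prognosis, and Protocol 7.3.2 lets treatment resume only if no progression was seen.
- *41.7% crosses the 40% (6/15) bar.* The criterion in Protocol 10.1 is a count of 6 patients, not a Kaplan-Meier percentage, and 5 event-free patients miss it either way. There is no formal hypothesis test.
- *All adverse events after radiation are lost.* They remain in the listing with a TEAE flag (SAP 17.1), on-treatment deaths are counted from the last dose (SAP 17.1.7), and one reading of the window keeps a further 30 (+7) days.

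**Conclusion.** The conflict is real and should be corrected before final database lock. SAP 14 contradicts Protocol 7.3.2 on whether on-study radiotherapy can be allowed. Followed as written, it applies censoring, scan-exclusion and TEAE rules to patients who are being managed within the protocol.

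The effect on PFS can go either way, and its size cannot be stated because no radiotherapy rate is given. Under the assumptions in step 3, two or three patients in a 15-patient arm shift the estimate by 5.1 or 8.3 percentage points (38.5 − 33.3 rounds to 5.1 unrounded; 41.7 − 33.3 to 8.3) without changing whether the count criterion is met. The safety effect is omission from the TEAE summaries, not from reporting. The finding assumes that on-study palliative radiation reaches the oncology radiotherapy form; that is the natural place for it but is not stated.

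**What to change.** In SAP 14, add a sentence saying that palliative radiotherapy permitted by Protocol 7.3.2, with study drug continued, is not new anti-tumor therapy and is not automatically a protocol deviation, and that the PFS, BOR, DoR and TEAE derivations run through it. Correct the premise that no on-study oncology therapy is allowed.

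Identify these records from the radiotherapy purpose field, which the SAP already summarises for prior radiotherapy, together with the dosing records. Confirm which CRF page holds them. State also what happens to a patient irradiated under this allowance who does not resume, because resumption itself depends on no progression having been seen, and a rule based on resumption alone would be selective.

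Optionally, report a PFS sensitivity analysis that censors at the radiation, so that a reader who prefers that rule can see the difference.

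The cost is a sentence or two and one programming flag. Data collection and clinical management do not change.
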